## **Aim and objectives**

**Aim:** To identify the optimum non-invasive test strategy that will robustly detect nAMD in fellow eyes during follow-up in secondary care of persons with nAMD in the first affected eye.

### **Objectives**

Primary objective: determine the diagnostic monitoring performance of the interventions (ETDRS visual acuity; fundus evaluation of signs of nAMD; the Amsler test; clinical assessment of images captured by OCT; patient's subjective assessment of vision against the reference standard of fundus fluorescein angiography);

Secondary objectives:

1. Develop an economic model to identify an optimal monitoring regime;
2. Develop a risk prediction model using baseline characteristics to predict the development of nAMD in the study eye;
3. Create a cohort (including a Bio bank) which can be used for future prognostic and diagnostic studies.

## **Design**

The study design is a multi-centre prospective cohort diagnostic accuracy study with 3 year follow-up. Once enrolled into the study, the participants will be monitored following standard clinical practice in the diseased eye. The standard of care in the NHS for patients newly diagnosed with nAMD is regular (approximately every 8 weeks) assessment and treatment if required. At each monitoring visit, patients will be examined using all index tests in the study eye (unaffected) and a reference standard measurement triggered if any of the index tests are positive. All patients will be followed-up according to standard clinical practice until confirmed treatment for nAMD in the study eye or until 3 years from enrolment, whichever is sooner. Patients who do not have confirmed nAMD in the study eye during the follow-up period will have a FFA at 18 months and exit. The study has been designed to have minimum impact on the current patient care pathway.

## **Statistical Principles**

### **Sample size**

The sample size is based upon comparative diagnostic accuracy to ensure the ability to detect differences in sensitivity and specificity between candidate tests. The calculation is based upon McNemar's test. (Obuchowski 1998) Under the primary analysis, a positive candidate test result will be defined as any positive result during the monitoring period on the respective test. At 2-sided 5% significance level and 90% power, a paired difference of 15% (80% to 65%) in sensitivity will require 491 participants (560 allowing for indeterminate/missing data results - including patients lost to follow-up cumulatively of up to 12%) given a cumulative incidence of 28% at 3 years. (Karnon 2008) This calculation assumes a disagreement between tests of 0.30 which was based upon data from a diagnostic study involving OCT for diagnosis glaucoma (HTA reference 09/22/111). A smaller difference in specificity will be identifiable (7%; 94% to 87% with power and significance levels as before) given most participants will not convert during the 3-year follow-up period even if the maximum level of disagreement occurs. The reference sensitivity and specificity values used in this calculation are the values observed for OCT in a pilot study with a similar study design. (Parnick-Silver 2012) Differences in sensitivity and specificity of at least 20% will also be detected at the same power and significance levels even if the sensitivities/specificity are substantially lower (e.g. 60 to 40%) or the level of missing data is higher (e.g. 20%). These calculations conservatively assume maximum possible disagreement between tests. A sample of this size would be of sufficient size for other measures of diagnostic performance (e.g. the sensitivity and specificity of individual technologies will be estimated to 95% confidence interval of width 16% and 10% respectively given a sensitivity/specificity of 65% or higher). Such a sample will also provide a sufficient sample for the GEE analysis given the anticipated gain in precision due to use of multiple repeated measures over

time. (Rochon 1998) Similarly, this sample will be more than sufficient for the development of a risk prediction model with over 130 events (conversions to AMD) anticipated and given 10 events per predictor variable/contract are typically recommended. (Peducci 1995).

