#### 7. SAMPLE SIZE, PROPOSED RECRUITMENT RATE, MILESTONES & INTERNAL PILOT

#### 7.1 Sample size

The sample size is based upon comparative diagnostic accuracy to ensure the ability to detect differences in sensitivity and specificity between candidate tests. The calculation is based upon McNemar's test. (Obuchowski 1998) Under the primary analysis, a positive candidate test result will be defined as any positive result during the monitoring period on the respective test. At 2-sided 5% significance level and 90% power, a paired difference of 15% (80% to 65%) in sensitivity will require 491 participants (560 allowing for indeterminate/missing data results - including patients lost to follow-up cumulatively of up to 12%) given a cumulative incidence of 28% at 3 years.(Karnon 2008) This calculation assumes a disagreement between tests of 0.30 which was based upon data from a diagnostic study involving OCT for diagnosis glaucoma (HTA reference 09/22/111). A smaller difference in specificity will be identifiable (7%; 94% to 87% with power and significance levels as before) given most participants will not convert during the 3-year follow-up period even if the maximum level of disagreement occurs. The reference sensitivity and specificity values used in this calculation are the values observed for OCT in a pilot study with a similar study design.(Parnick-Silver 2012) Differences in sensitivity and specificity of at least 20% will also be detected at the same power and significance levels even

if the sensitivities/specificity are substantially lower (e.g. 60 to 40%) or the level of missing data is higher (e.g. 20%). These calculations conservatively assume maximum possible disagreement between tests. A sample of this size would be of sufficient size for other measures of diagnostic performance (e.g. the sensitivity and specificity of individual technologies will be estimated to 95% confidence interval of width 16% and 10% respectively given a sensitivity/specificity of 65% or higher). Such a sample will also provide a sufficient sample for the GEE analysis given the anticipated gain in precision due to use of multiple repeated measures over time.(Rochon 1998) Similarly, this sample will be more than sufficient for the development of a risk prediction model with over 130 events (conversions to AMD) anticipated and given 10 events per predictor variable/contract are typically recommended.(Peducci 1995)

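### The 7-point specificity difference has 90% power only if all 560 recruited participants are evaluable; with the plan's own 491 the power is 86%

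*SAP*

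**What the plan says.** The sample size paragraph is the same in the SAP (Statistical Principles, Sample size) and in protocol section 7.1. It names the test: "The calculation is based upon McNemar's test". It sets the sample from sensitivity: "At 2-sided 5% significance level and 90% power, a paired difference of 15% (80% to 65%) in sensitivity will require 491 participants", "given a cumulative incidence of 28% at 3 years". For that comparison, "This calculation assumes a disagreement between tests of 0.30". The recruited total is then given as "560 allowing for indeterminate/missing data results - including patients lost to follow-up cumulatively of up to 12" per cent.

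For specificity it adds: "A smaller difference in specificity will be identifiable (7%; 94% to 87% with power and significance levels as before". It says this holds "even if the maximum level of disagreement occurs". A later sentence repeats that the calculations take the greatest disagreement that could arise and calls this conservative. No denominator and no numerical disagreement are given for the specificity figure.

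The SAP (Analysis A) builds the McNemar table for specificity only from participants whose FFA results are negative throughout. It excludes anyone without a follow-up FFA.

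**The concern.** The paragraph separates 491 participants needed for analysis from 560 to be recruited. The specificity statement follows without saying which of the two it uses. Participants without a valid follow-up FFA cannot enter the specificity table, so the evaluable number is the natural basis. The stated 7 points at 90% power seems to need the recruited number.

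Sensitivity and specificity are both primary diagnostic outcomes, and the paragraph says the sample is meant to secure comparisons of both. If two tests differ by about 7 points in specificity and the result is not significant, readers will judge it against a stated 90% power that is described as conservative. The SAP (Interim analyses) also has the steering committee monitor between-test disagreement as a check on the sample size assumption. For specificity, that check has no stated value to compare with.

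**Working it through.** **Inputs (SAP, Sample size; same text in protocol 7.1).** Two-sided 5%, so z = 1.960. Power 90%, so z = 1.2816. Cumulative incidence 28%, so 72% are non-converters. Evaluable 491, recruited 560, loss up to 12%. Sensitivity 80% v 65% with disagreement 0.30. Specificity 94% v 87% at maximum disagreement.

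**Formulas (McNemar, normal approximation; d = difference, ψ = disagreement).**
- n = [1.960·√ψ + 1.2816·√(ψ − d²)]² / d²
- power = Φ{ [d·√n − 1.960·√ψ] / √(ψ − d²) }

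**1. The plan's sensitivity figure.** With d = 0.15 and ψ = 0.30, n = 135.9, so 136 converters, and 136/0.28 = 486. The plan states 491, so the method follows the plan's to within about 1%. Also 491/0.88 = 558, against the stated 560.

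**2. The plan's specificity figure.** Disagreement is largest when no participant is a false positive on both tests: ψ = 0.06 + 0.13 = 0.19. With d = 0.07:
- 1.960 × √0.19 = 0.8543
- 1.2816 × √(0.19 − 0.0049) = 0.5514
- n = (0.8543 + 0.5514)² / 0.0049 = 403.3 non-converters
- 403.3/0.72 = 560.1 participants

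The 90% is therefore reproduced at 560 with no loss: 560 × 0.72 = 403.2 non-converters gives power 90.0%.

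**3. The same claim at the evaluable number.** 491 × 0.72 = 353.5 non-converters. Then (0.07 × √353.5 − 0.8543)/0.4302 = 1.073, and Φ(1.073) = 0.859.

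| Evaluable N | Non-converters | Power for 7 points (ψ = 0.19) | Difference from 94% detectable at 90% power |
|---|---|---|---|
| 560 (no loss) | 403.2 | 90.0% | 7.0 points |
| 491 | 353.5 | 85.9% | 7.6 points |
| 448 (20% missing) | 322.6 | 82.6% | 8.0 points |

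In the last column ψ is the maximum for each difference, 0.12 + d.

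**4. Does the choice of McNemar variant matter?** At 491 and ψ = 0.19, other two-sided versions (continuity-corrected, exact, mid-p, exact power of the asymptotic test) give 83.6% to 86.7%. A one-sided test would give 91.8%, but the plan is two-sided.

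**5. What 7 points at 90% would need.** 404 non-converters, which is 404/0.72 = 561 evaluable, or 561/0.88 = 638 recruited.

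**The case against.** Four points can be made for the plan.

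- **The denominator is not stated.** Other figures in the paragraph fit 491. At 65%, the confidence interval widths are 15.9% with 137 converters and 9.9% with 354 non-converters, as stated (16% and 10%); at 560 they would be 14.9% and 9.3%. So the use of 560 is an inference. This stands, but at 491 the 90% is missed whatever the sponsor's route to the figure.
- **Maximum may have meant independence between tests.** Then ψ = 0.94 × 0.13 + 0.06 × 0.87 = 0.1744, power at 491 is 88.7%, and the detectable difference is 7.2 points, which rounds to 7. The paragraph's 60% to 40% statement favours this reading for sensitivity: at 491, power is 91% with ψ = 0.52 (independence) but 65% with ψ = 1.0 (the true maximum). However, independence is not the maximum that the text names twice, and 90% would still need 514 evaluable. On this reading the wording is what needs correcting.
- **Late losses may still count.** A participant lost after a negative 18-month or triggered FFA still enters as reference-negative, so actual power could lie between 86% and 90%. The timing of losses is not given, and the paragraph itself defines 560 as 491 plus the allowance.
- **The effect is small.** This stands. With 354 non-converters, 90% power holds if disagreement is about 0.167 or lower.

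**Conclusion.** The concern holds. On the plan's own inputs, taken literally (ψ = 0.19, two-sided 5%, 28% incidence, 491 evaluable), power for a 7-point specificity difference is 86%, not 90%, and the difference detectable at 90% power is 7.6 points. The stated figure is met only with 560 evaluable participants, which leaves no room for the plan's 12% allowance. That the sponsor used 560 is inferred from a near-exact match (560.1). That 491 falls short is arithmetic, and it remains true under independence (88.7%). The error is modest: it affects a descriptive power statement for one of two primary accuracy measures. It changes neither the recruitment target nor any analysis.

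**What to change.** In the SAP (Sample size) and protocol section 7.1, state the evaluable number and the disagreement behind the specificity figure, and correct the figure to match. For example:

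> With 491 evaluable participants (354 non-converters) and maximum disagreement between tests (0.19 for 94% v 87%), power to detect a 7-point difference in specificity is 86%; a difference of 7.6 points (94% to 86.4%) is detectable with 90% power.

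If the sponsor meant another disagreement value, such as independence, it should give that value, drop the word maximum, and quote the figures that follow (at independence: 88.7% power for 7 points, 7.2 points at 90%).

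The cost is one sentence in each document and a slightly less favourable figure. No extra recruitment is needed.

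### The 90% power claimed for a 20-point difference in sensitivity does not hold at maximum disagreement: at 60% v 40% it is about 65%

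*SAP*

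**What the plan says.** The SAP (Sample size) and Protocol 7.1 carry the same paragraph. "The calculation is based upon McNemar's test", and the headline case is: "At 2-sided 5% significance level and 90% power, a paired difference of 15% (80% to 65%) in sensitivity will require 491 participants", "given a cumulative incidence of 28% at 3 years". For that case the discordance is stated: "This calculation assumes a disagreement between tests of 0.30". The total is then raised to "560 allowing for indeterminate/missing data results - including patients lost to follow-up cumulatively of up to 12" per cent.

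A supplementary claim follows: "Differences in sensitivity and specificity of at least 20% will also be detected at the same power and significance levels". It is said to hold if accuracy is much lower (60% v 40% is the example) or if missing data reach 20%. No discordance value is given for this second calculation. The next sentence is "These calculations conservatively assume maximum possible disagreement between tests".

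Under Interim analyses, the SAP has the steering committee monitor the disagreement between tests, blinded to individual results, as a check on the key sample-size assumption.

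**The concern.** The power of McNemar's test for a given difference falls as discordance rises. To say that a power figure already assumes the largest possible discordance is to say that no pattern of agreement could make it worse. For the sensitivity comparison, which uses converters only, that can be checked from the plan's own inputs, and it fails.

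At stake is how the sensitivity comparisons are read. Someone who takes the sentence at face value would think that 20-point differences are safe whatever the agreement between tests. They would then have little reason to react if the planned monitoring showed high disagreement.

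**Working it through.** **Inputs (SAP, Sample size)**

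- Two-sided 5%: z = 1.960. Power 90%: z = 1.2816.
- Converters: 491 x 0.28 = 137 at the plan's own allowance for loss; 560 x 0.80 x 0.28 = 125 with 20% missing data; 560 x 0.28 = 157 with no loss.
- Non-converters: 491 x 0.72 = 354; 560 x 0.80 x 0.72 = 323.
- 60% v 40% is the plan's example. 80% v 60% is my reading of a 20-point difference from its 80% reference sensitivity.

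**Formulas** (d = difference, psi = discordance)

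- Number needed: n = [1.960 sqrt(psi) + 1.2816 sqrt(psi - d^2)]^2 / d^2
- Power = Phi{[d sqrt(n) - 1.960 sqrt(psi)] / sqrt(psi - d^2)}
- Largest psi the margins allow: min(p1, 1 - p2) + min(p2, 1 - p1)
- psi for independent tests: p1(1 - p2) + p2(1 - p1)

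**Step 1. Headline case.** With d = 0.15 and psi = 0.30, n = (1.0735 + 0.6751)^2 / 0.0225 = 135.9, so 136 converters. 136 / 0.28 = 486, against 491 stated. 491 / 0.88 = 558, against 560 stated. Both agree closely, so the formula suits this plan.

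**Step 2. 60% v 40% at the maximum.** Maximum psi = 0.60 + 0.40 = 1.00. n = (1.960 + 1.2816 x 0.9798)^2 / 0.04 = 258.5, so 259 converters, or 259 / 0.28 = 925 evaluable participants. With 137 converters, power = Phi[(0.20 x 11.705 - 1.960) / 0.9798] = Phi(0.389) = 65%. Enumerating the test distribution at 137 gives 62% for the exact test and 68% for the uncorrected or mid-p test.

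**Step 3. Power for a 20-point difference in sensitivity**

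| Margins | psi | 137 converters | 125 (20% missing) | 157 (no loss) |
|---|---|---|---|---|
| 60 v 40 | 1.00 (maximum) | 65% | see objection | 71% |
| 60 v 40 | 0.52 (independence) | 91% | 88% | 94% |
| 80 v 60 | 0.60 (maximum) | 86% | 83% | 91% |
| 80 v 60 | 0.44 (independence) | 95% | 93% | 97% |

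**Step 4. Limit for 90% power.** Solving the power formula for psi at d = 0.20 gives about 0.54 with 137 converters and about 0.49 with 125.

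**Step 5. Specificity at 60% v 40%, psi = 1.00.** With 354 non-converters, power = Phi[(0.20 x 18.815 - 1.960) / 0.9798] = Phi(1.84) = 97%. With 323 it is 95%. This half of the claim holds as written.

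**The case against.** The strongest reply is that the 90% was probably calculated at independence. With psi = 0.52 the 60% v 40% case gives 91%, and 80% v 60% with 20% missing data gives 93%. A discordance of 1.00 would mean that every converter is positive on exactly one of two tests of the same eye, which is implausible. Unless the tests are negatively related, independence is the ceiling. Much of this stands: a reader might infer that the 90% is itself a miscalculation, and the documents do not show that.

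The stated condition remains wrong. Independence is not the maximum, the text never defines it so, and it gives no value. Nor can the literal reading be set aside. At their literal maxima, 80% v 60% (0.60) gives 91% and the plan's 94% v 87% specificity case (0.19) gives 90%, provided all 560 are analysed without loss. The 60% v 40% sensitivity case fails even then, at 71%.

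Three further inferences are tempting but not supported.

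- **About 61% power**, from combining 60% v 40% with 20% missing data at the maximum. The plan offers these as alternatives, so 65% is the relevant figure for its example.
- **That the 15-point calculation is contradicted.** It discloses its 0.30 and the source. The sentence on maximum disagreement follows the 20-point claim and most naturally refers to that. For 80% v 65%, 0.30 is below independence (0.80 x 0.35 + 0.65 x 0.20 = 0.41), but that is a declared assumption.
- **That the whole sentence should go.** That would remove a correct statement about specificity.

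The planned monitoring of disagreement is a partial safeguard, but the plan sets no discordance limit for the 20-point claim.

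**Conclusion.** The concern holds for sensitivity only. The 90% power for a 20-point difference is not true under the condition attached to it: about 65% at 60% v 40%, and about 86% (83% with 20% missing data) at 80% v 60%. It is true up to a discordance of about 0.54, or about 0.49 with 20% missing data, so roughly for independent tests. The 20-point specificity claim at 60% v 40% is sound.

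These figures assume 28% incidence among evaluable participants, the plan's allowance for loss, and the normal approximation to McNemar's test. At 60% v 40% and maximum disagreement, other versions of the test give 62% to 68%.

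A reader might infer that the study is too small. The documents do not support that: 491 and 560 reproduce, and they come from the 15-point calculation, not from this sentence. The correction should be made, but it changes no test, estimand or target.

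**What to change.** In SAP Sample size and Protocol 7.1:

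1. For the 20-point sensitivity claim, replace the sentence "These calculations conservatively assume maximum possible disagreement between tests" with the discordance actually used. State that 90% power needs a discordance of at most about 0.54 (about 0.49 with 20% missing data), and that power is about 65% at the true maximum for 60% v 40%.
2. Keep the maximum-disagreement wording only for the 20-point specificity claim.
3. Say that it does not cover the 15-point calculation, which uses 0.30.
4. Use these limits as reference values for the disagreement monitoring already planned under SAP Interim analyses.

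The cost is wording in two documents and less favourable stated figures. No more participants are needed, and 491 and 560 stay as they are.

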**Analysis Objective 2: To develop a risk prediction model**

**Analysis D. Prognostic modelling.** A risk prediction model using Cox regression will be developed to predict development of nAMD (using the clinical reference standard – see reference standard definition C above in table 3) in the EDNA study eye using baseline risk factors. Appendix 1 shows the table of risk factors which will be considered for inclusion in the model. The model’s predictive performance will be assessed in terms of discriminative and calibrative ability. Discriminative ability will be assessed using Harrell’s *c*-index. Calibration will be assessed by plotting the average predicted risk compared with the corresponding Kaplan-Meier estimate of the observed risk by tenth of predicted risk. Recalibration of the model will be undertaken via adding/removing predictors if necessary. Internal validation will be undertaken using a bootstrapping approach. (Moons 2012).

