**Table of planned factors for prognostic analysis**

Unit of analysis (EYE if applicable or PERSON)	Name of factor
PERSON	Age
PERSON	Raised blood pressure
PERSON	Smoking history
PERSON	Cardiovascular disease
PERSON	Diabetes
PERSON	Gender
PERSON	Nutritional supplements
PERSON	Family history of AMD
PERSON	BMI
FELLOW EYE	Type of wet AMD in fellow eye (CNV/RAP)
FELLOW EYE	Severity of nAMD from the baseline non-EDNA eye
EDNA eye	Previous cataract surgery
EDNA eye	VA at baseline in EDNA eye
EDNA eye	Type of drusen at baseline EDNA eye
EDNA eye	Maximum size of drusen at baseline EDNA eye
EDNA eye	Most frequent size of drusen at baseline EDNA eye
EDNA eye	presence of pigmentary abnormalities in the fundus of the study eye
EDNA eye	Retinal thinning present
EDNA eye	Choroid thinning
EDNA eye	ELM disruption
EDNA eye	EZ disruption

## Appendix 2

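### The SAP's adequacy claim for the risk model does not fit its own list: 21 candidate factors give about 6.5 events each against its rule of 10, and the bootstrap's handling of predictor changes is left open

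*SAP*

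**What the plan says.** The SAP (Sample size) states that "this sample will be more than sufficient for the development of a risk prediction model with over 130 events (conversions to AMD) anticipated", and gives as its ground "given 10 events per predictor variable/contract are typically recommended". It does not say how many predictors it had in mind. The same sentence stands in Protocol Section 7.1. Protocol Section 8 names 11 risk factors: age, blood pressure, smoking, obesity and ethnicity; type, size and number of drusen; pigmentary abnormalities; and type and severity of disease in the first eye.

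SAP Analysis D fits a Cox model and takes its candidates from Appendix 1, the "Table of planned factors for prognostic analysis". That table has 9 person-level, 2 fellow-eye and 10 study-eye rows, 21 in all. Protocol Section 8 gives the analysis plan precedence where the two differ, so the longer list governs.

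Analysis D adds that "Recalibration of the model will be undertaken via adding/removing predictors if necessary". It gives no criterion for those changes, and no penalisation or shrinkage. Internal validation is by bootstrap, without saying which modelling steps each resample repeats. The missing-data section allows multiple imputation of baseline variables and does not link it to the bootstrap.

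**The concern.** The only support offered for the risk model's sample size is a rule of 10 events per predictor, and the SAP's candidate list is too long for it. A Cox model fitted without shrinkage to too many candidates predicts risks that are too extreme: too high for high-risk patients and too low for low-risk ones.

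The second part concerns how performance will be reported. Adding or dropping predictors after looking at calibration changes the model using the same data. Recalibration normally leaves the predictors alone and rescales the predictions. If the bootstrap starts from the finished model, the selection escapes the optimism correction, and the c-index and calibration look better than they are.

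The model is a named secondary objective. Protocol Section 10 intends it for risk assessment and for informing the monitoring interval, and Protocol Section 9 feeds the risk-model results into the economic model.

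**Working it through.** **1. The plan's own figures.** Inputs (SAP, Sample size): "At 2-sided 5% significance level and 90% power", difference d = 0.15, disagreement psi = 0.30, "given a cumulative incidence of 28% at 3 years".

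- McNemar, diseased participants: (1.96 x sqrt(0.30) + 1.2816 x sqrt(0.30 - 0.15^2))^2 / 0.15^2 = 135.9, so 136.
- Total: 136/0.28 = 486, against the stated 491 (1.0% apart).
- Loss: 491/0.88 = 558, against 560.
- Events: 491 x 0.28 = 137.5.

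So the statement of over 130 events reproduces.

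**2. Events per factor.** Events divided by candidate factors, each counted as one parameter:

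| Basis | Events | Per factor, 11 (protocol) | Per factor, 21 (SAP) | Parameters allowed at 10 each |
|---|---|---|---|---|
| Stated minimum | 130 | 11.8 | 6.2 | 13 |
| 491 x 28% | 137 | 12.5 | 6.5 | 13 |
| 560 x 28%, no loss | 157 | 14.3 | 7.5 | 15 |

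The SAP background gives 8-10% conversion a year. Over three years, 1 - 0.92^3 = 22.1% and 1 - 0.90^3 = 27.1%. With 491 participants that is 109 to 133 events, or 5.2 to 6.3 per factor.

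**3. What the rule would need.** 21 x 10 = 210 events. That is 210/0.28 = 750 evaluable participants, or 750/0.88 = 853 recruited. At the planned size it would take 210/491 = 43% converting, or 210/560 = 37.5%.

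**4. Why 21 is a minimum.** The baseline dummy table shows smoking as current, ex or never, which takes two parameters. That alone gives 22 parameters, and 137/22 = 6.2.

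**5. Consequence for the predictions (assumed inputs).** The usual shrinkage formula, n = p / ((S - 1) ln(1 - R2/S)), was solved for S with n = 491 and 137 events. R2 was taken as 15-30% of its maximum of 0.694; the documents give no value. Expected S is 0.72-0.85 with 21 parameters, 0.81-0.90 with 13 and 0.83-0.91 with 11. Holding R2 fixed somewhat flatters the shorter lists, since dropped factors may carry signal.

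**6. What the bootstrap must repeat (simulation on assumed inputs).** There were 60 data sets of 491, about 28% events, and 21 independent normal factors, 5 of them real with log hazard ratio 0.25 per SD.

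- All 21 forced in: c-index 0.677 apparent and 0.624 in new data; calibration slope 0.66.
- Backward elimination at p = 0.05: c-index 0.659 apparent and 0.629 in new data; slope 0.80.
- In the 15 eliminated models that were bootstrapped, true optimism in the c-index averaged 0.036. A bootstrap repeating the elimination estimated 0.038; one that only refitted the final model estimated 0.012, a third of the truth.

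Backward elimination stands in for the add/remove step, whose criterion the SAP does not give.

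**The case against.** The Appendix 1 factors are only to be considered for inclusion, and the rule is worded per predictor, not per candidate parameter. A final model of five or ten predictors would satisfy it literally. Counting candidates is our reading. It is the sound one, because choosing among candidates uses the data; and as the SAP sets no limit on the final model, all 21 could stay.

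The event count is also not fixed. A Cox model uses people lost early up to censoring, and Analysis D counts clinical diagnoses as well as positive angiograms, so events may exceed 137. That is fair, and a range is given. Reaching 210 would need about half as many again (210/137 = 1.53), which the SAP does not claim.

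Several stronger readings are tempting but not supported:

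- A reader might infer that the add/remove step itself makes the model overfit more. The simulation points the other way: elimination gave a slope of 0.80, against 0.66 with all 21 forced in. The risk is optimism that goes unmeasured.
- A reader might infer that the planned bootstrap is wrong. The SAP is silent on what it repeats and does not rule selection out; the predictor changes themselves are planned only if needed.
- A reader might put the parameter count at 25-30. Only smoking is shown with several levels. Coding of drusen type, drusen size and severity is not given, and some could be single continuous terms.

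**Conclusion.** The adequacy statement is wrong as written for the SAP's list. Its event count is right. Under its own rule, applied to candidates, the sample supports about 13 parameters (15 at best), and the SAP lists at least 21. Events per factor are 6.2-6.5 on the planned figures, and between 5.2 and 7.5 across the other event counts considered; none reaches 10. The claim did hold for the protocol's 11 factors, each counted once. The likeliest explanation, an inference, is that the sentence was carried over while the list grew.

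The bootstrap point is conditional: optimism will be understated if only the final model is validated, and the SAP does not say which is done. The shrinkage and simulation figures show direction and rough size under assumed inputs and do not predict this study's results.

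A reader might take this as a flaw in the study's sample size. It is not: the 560 rest on the paired comparison of sensitivities, which this leaves untouched, as it does the primary accuracy analysis.

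**What to change.** 1. In the SAP's sample-size section, replace the adequacy claim with the number of candidate parameters, as coded, and the expected events per parameter with their range.
2. Before predictor-outcome data are examined, either reduce the candidates to about 13 parameters on subject-matter grounds, or fit a penalised Cox model to all of them. Unblinding cannot serve as the deadline, since Protocol Section 11.5 says the study has no blinding.
3. Drop the adding and removing of predictors as a form of recalibration. Shrink the predictions by the bootstrap calibration slope instead. If predictors are to be selected, state the method and criterion as a separate step.
4. State that every modelling step, including selection and any imputation, is repeated in each bootstrap sample, and report the optimism-corrected c-index and calibration slope.

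The cost is SAP wording and standard software, with no new data. Reported performance may look slightly worse.
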